3. STUDY CONDUCT

3.1 RANDOMIZATION ISSUES

After completing the informed consent form, eligible patients will be enrolled into the study and randomized using a central Interactive Voice/Web Response System (IxRS). Patients will be randomly allocated to receive RTX plus MMF placebo or RTX placebo plus MMF in a 1:1 ratio. Randomization will be performed according to a stratified permuted block design using the two baseline stratification factors (duration of illness [diagnosed \leq 1 year from screening versus $>$ 1 year] and geographical region [North America vs Rest of World]).

A mock randomization schedule was generated by the IxRS vendor () and user acceptance testing was performed on the IxRS system for both voice and web based methods. Testing of the system by the Sponsor's study statistician confirmed the following: correct strata and block allocation, correct treatment assignment, and agreement between IxRS output and the IxRS datasets delivered to the Sponsor.

The independent Data Coordinating Center (iDCC) will perform one round of randomization checks early during the recruitment period. The checks will be similar to those performed during user acceptance testing and will be carried out no later than when 30% patients have been randomized. The iDCC will notify the Sponsor's study statistician of any potential issues. Further checks at additional time points may be performed if necessary.

Rituximab—F. Hoffmann-La Roche Ltd
9/Statistical Analysis Plan WA29330

3.2 DATA MONITORING

Safety data and data pertaining to trial conduct will be reviewed by an independent Data Monitoring Committee (iDMC). The iDMC will meet according to the schedule below, whichever occurs first:

- After the first 10 patients have completed at least 3 months of study treatment or have withdrawn early from the study
- After the first 5 TM patients have completed at least 3 months of study treatment or have withdrawn early

Thereafter, meetings will be held approximately every 4 or 6 months (frequency may be adjusted during the recruitment period), after 10 TM patients have completed at least 3 months of study treatment or withdrawn early from the study, or as requested by the iDMC.

Efficacy data will be available on request, to enable a benefit-risk assessment should there be a safety concern.

The Sponsor's study team will have no direct contact with the iDMC during the trial conduct except for the scheduled open sessions of the iDMC.

Further details can be found in the iDMC charter.

4. STATISTICAL METHODS

All analyses, summaries, and listings will be performed using SAS[®] software (Version 9.2 or later).

4.1 ANALYSIS POPULATIONS

All patient populations for the analysis of the 52-week, double-blind treatment period will be defined and documented prior to unblinding the data collected up to Week 52.

4.1.1 Randomized Population

The randomized population will include all patients randomized into the study.

4.1.2 Pharmacokinetic-Evaluable Population

The pharmacokinetic-evaluable population (PK population) will include all patients randomized to and received any dose of RTX given as study medication, have at least one post-dose PK sample that is evaluable, and have no major protocol deviations that would impact the PK results.

4.1.3 Safety Population

The safety population will include all patients who were randomized and received any part of an infusion of study drug or oral administration of study drug. Patients who received the incorrect treatment throughout the study from that assigned at

Rituximab—F. Hoffmann-La Roche Ltd
10/Statistical Analysis Plan WA29330

randomization will be reported under the treatment actually received. Patients who were not randomized but who received study drug will be included in the safety population and reported under the treatment actually received.

Patients receiving at least one dose of both active study treatments during the study (e.g., in error, or in the unlikely event of crossing over) will be reported under the original treatment received. This does not include MMF or RTX received as rescue therapy.

All safety analyses including AEs, in addition to analysis of previous and concomitant medications, previous and concomitant diseases, laboratory data, and compliance with study treatment, will be performed using the safety population.

4.1.4 Intent-to-Treat Population

The intent-to-treat (ITT) population will include all randomized patients who received any part of an infusion of study drug or oral administration of study drug.

Patients who prematurely withdraw from the study for any reason and for whom an assessment is not performed for whatever reason will still be included in the ITT analysis. Patients who received an incorrect therapy (i.e., different from that to which they were randomized) will be summarized in the treatment arm to which they were randomized.

Patients with no post-baseline data will still be included in the ITT population but will have their efficacy results imputed according to the imputation methods described in this SAP for all key efficacy assessments.

Patients who were not randomized but still received study treatment will be excluded from the ITT population and subsequent analyses.

Sensitivity analyses of the efficacy outcomes will be performed using the ITT population.

4.1.5 Modified Intent-to-Treat Population

The modified intent-to-treat population (mITT) population includes patients in the ITT population, excluding the 10 TM patients. This population will be used in the analyses of efficacy outcomes.

4.2 TREATMENT FAILURE

Treatment failure is the occurrence of any one of the following events:

- After disease control has been achieved, a two-step increase in prednisone (or equivalent) dose to ≥ 20 mg/day for more than 2 weeks to treat increased disease activity during the corticosteroid taper
- Failure to achieve disease control after receiving 240 mg/day oral prednisone (or equivalent) for 1 week

Rituximab—F. Hoffmann-La Roche Ltd
11/Statistical Analysis Plan WA29330

Disease control is defined as the time at which new lesions cease to form and established lesions begin to heal (beginning of the consolidation phase).

- Increase in MMF/matching placebo dosage above 2 g/day
- Initiation of any rescue therapy (addition of another immunosuppressive medication, additional RTX or MMF open-label doses, intravenous (IV) Ig, plasmapheresis, or another treatment or procedure) as determined by the investigator's best medical judgment

The clinical definitions of treatment failure above are aligned with "non-responder" classification for the primary analysis. Patients experiencing treatment failure prior to achieving sustained complete remission will be categorized as non-responders in the primary analysis, but will continue to be followed in the study per the schedule of assessments. Patients who achieve sustained complete remission without experiencing an event constituting treatment failure beforehand will not be categorized as non-responders, regardless of whether they subsequently meet the criteria during the remaining treatment period.

Patients who experience treatment failure will be analyzed using data up to the point of treatment failure for efficacy remission endpoints, including the primary endpoint for sustained complete remission.

From Week 12 through Week 52, patients who experience treatment failure are eligible to receive rescue therapy during the treatment period with another immunosuppressive medication, IV Ig, plasmapheresis, or another treatment or procedure as per the investigator's best medical judgment. An early withdrawal visit is not required for a patient to receive rescue therapy, and patients should continue to be followed in the study per the 52-week treatment period (see [Appendix 1](#)).

Patients who receive rescue therapy will be evaluated up to the point of rescue only for all main efficacy analyses. Methods for data handling and/or imputing post-rescue data are described throughout Section 4.7. Additional exploratory summaries on key efficacy assessments will be produced that will include rescue data. Safety analyses will include data up to the point of rescue only.

Listings will include all data, including data post-rescue treatment.

Depending on the proportion of patients receiving rescue, patients will be analyzed separately using descriptive statistics for key analyses on study conduct, efficacy, and safety. For relevant summaries, patients may be re-baselined at the time of rescue and data presented as pre- and post-rescue treatment. Rescue analyses will use data as observed. Subject to patient counts, a limited number of analyses may be summarized by type of rescue received (MMF given as rescue, RTX given as rescue, or other).

Rituximab—F. Hoffmann-La Roche Ltd
12/Statistical Analysis Plan WA29330

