All patients who withdraw from the treatment period or who complete the total 52-week treatment period must return for post-*Week 52* SFU assessments at 12, 24, 36, and 48 weeks after either the early withdrawal visit or study treatment completion, respectively. Thus, patients will be followed for approximately 1 year in the SFU period. A schedule of assessments during the SFU period is provided in [Appendix 2](#).

Before Week 12, patients who experience treatment failure (as defined in Section [3.1.3](#)) will require an early withdrawal visit and will be followed in the SFU period to receive standard-of-care treatment per the investigator's best medical judgment.

From Week 12 through Week 52, patients who experience treatment failure (as defined in Section [3.1.3](#)) are eligible to receive rescue therapy during the treatment period with another immunosuppressive medication, IV Ig, plasmapheresis, or another treatment or procedure as per the investigator's best medical judgment. An early withdrawal visit is not required for a patient to receive rescue therapy, and patients should continue to be followed in the study per the 52-week treatment period (see [Appendix 1](#)).

If a patient receives rescue therapy with rituximab, the number and timing of infusions will be at the discretion of the investigator. Every effort will be made to maintain the study blind, but the patient may be unblinded at the discretion of the Principal Investigator's safety assessment. Patients who receive rescue infusions with rituximab from Week 12 through Week 24 will not receive the scheduled rituximab or matching placebo infusions on Days 168 and 182. Careful consideration should also be given as to whether MMF/matching placebo are continued following rescue therapy with any immunosuppressive medication.

Evaluation of the primary endpoint will occur at Week 52. To prevent potential unblinding due to observed efficacy or laboratory changes, a dual-assessor approach will be used to evaluate efficacy and safety.

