In RA, the rituximab dose 2×1000 mg IV (Days 1 and 15) has been demonstrated to be an effective dose, sufficient to sustain B-cell depletion for 6–9 months. Achieving other therapeutic outcomes in PV, such as complete removal of autoantibodies via sustained B-cell depletion in both the periphery and secondary lymphoid organs, is also a target in the management of PV. Sustained complete remission is the ultimate therapeutic goal. A single cycle of rituximab, although generally effective for at least 6 months (24 weeks), is not considered a cure in this autoimmune-relapsing disease. In RA, it is recommended that, until the desired treatment target is reached, drug therapy should be repeated at least every 6 months ([Smolen et al. 2010](#)). Additionally, a recent clinical trial investigating the use of rituximab in patients with severe and/or refractory pemphigus (84 PV patients; 8 pemphigus foliaceus patients) showed that patients who do not achieve remission after 1 cycle and those who experience relapse benefit from further cycles of rituximab. This recent study suggested that the majority of PV patients receiving a single cycle of rituximab will experience a disease flare, further supporting the rationale for an additional treatment cycle at 6 months ([Heelan et al. 2014](#)).

Rituximab—F. Hoffmann-La Roche Ltd
36/Protocol WA29330, Version 5

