6. STATISTICAL CONSIDERATIONS AND ANALYSIS PLAN

Full details of all statistical methods and planned statistical analyses will be specified in the Statistical Analysis Plan (SAP), which will be finalized prior to locking and unblinding of the database. All efficacy outcomes will be analyzed according to the *modified intent-to-treat (mITT) population* and will include all randomized patients, *with exception of TM patients*, who have received any amount of study drug.

Treatment period data will be locked after all patients have completed the Week 52 visit. The primary efficacy (*excluding TM patients*) and safety analyses will be performed on data for patients through the Week 52 assessments or early discontinuation. A final database lock will occur after all patients have completed the trial, including the SFU period.

Safety assessments will be performed on patients who are evaluable for safety. In all safety analyses, patients will be grouped according to the treatment received rather than the treatment assigned.

Every effort will be made to obtain all scheduled efficacy and safety assessments for each patient. Patients who miss any scheduled doses or assessments will continue participation in the study and will continue to receive study drug.

Primary imputation methods for missing data will be specified in the SAP.

As part of a sensitivity analysis, *the inclusion of TM patients*, missing data patterns and associated missing data mechanisms will be further explored and analyzed as appropriate. The assumptions and methodology will be specified in SAP.

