4.9 SAFETY ANALYSES

The safety analysis will be performed on the safety population as defined in Section 4.1.3. Analyses of safety data up to Week 52 will include rescue patients up to the point of rescue only. Post-rescue data for patients who receive rescue therapy will be summarized separately for selected key safety outputs.

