4.9.2 Adverse Events

Adverse events will be mapped and reported using the Medical Dictionary for Regulatory Activities (MedDRA) thesaurus using the most current version at the time of analysis (version 17.1 or later). Glossaries showing the mapping of investigator verbatim terms to coded events will be produced.

A listing of AEs occurring during screening (prior to Day 1) will be produced to capture AEs occurring during the oral corticosteroid taper.

Treatment-emergent AEs (TEAEs) will be summarized. All AEs referenced in the section below will be TEAEs. TEAEs are defined as those AEs with observed or imputed onset date on or after the start date of trial treatment. Only where the most extreme intensity is greater than the initial intensity (or if most extreme intensity is not missing and initial intensity is missing) will events with an onset date prior to the start of trial treatment be considered treatment-emergent. An AE with a completely missing start date will be assumed to be treatment-emergent unless the AE has a complete non-imputed end date that is prior to study Day 1.

Listings will show all AEs reported, including AEs occurring after rescue therapy, and any AEs that may have occurred during the oral corticosteroid dose adjustments in the screening period.

AEs will be summarized by system organ class (SOC) and preferred term (PT), and will be presented in order of descending frequency summed across the treatment arms within each SOC and PT.

The following will be summarized, and/or listings produced where required:

- AEs
- Serious Adverse Events (SAEs)
- AEs by relationship to study medication
- AEs leading to study drug dose modification or interruption
- AEs by common terminology criteria grade
- Infections
- Serious Infections
- Corticosteroid-related AEs
- Infusion related reactions (IRRs) (Roche Standard AE Grouped Term [AEGT] MedDRA Basket)
- Serious IRRs
- AEs leading to withdrawal

Rituximab—F. Hoffmann-La Roche Ltd
31/Statistical Analysis Plan WA29330

- AEs leading to death
- Opportunistic infections (OI) , including serious OI (Roche Standard AE Grouped Term [AEGT] MedDRA Basket for Opportunistic Infections)

If an imbalance in exposure is found between treatment groups, AE rates per 100 patient-years exposure may be calculated. AE rate per 100 patient-years is defined as:

$$(\text{number of events} \div \text{total exposure}) \times 100$$

The 95% CIs will be calculated based on exact X^2 distribution.

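### The Week 52 safety tables stop at rescue, a cut the protocol does not state, so no planned table counts patients per arm with an event over the full 52 weeks

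*SAP*

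**What the plan says.** The SAP sets the rule twice. Section 4.2 has "Safety analyses will include data up to the point of rescue only", and section 4.9 has "Analyses of safety data up to Week 52 will include rescue patients up to the point of rescue only". For what follows rescue, 4.9 adds: "Post-rescue data for patients who receive rescue therapy will be summarized separately for selected key safety outputs". It does not name those outputs, and 4.2 makes the separate analysis of rescued patients depend on how many there are.

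Listings are complete. Section 4.2 says "Listings will include all data, including data post-rescue treatment", section 4.9.2 says "Listings will show all AEs reported, including AEs occurring after rescue therapy", and section 4.9.3 lists every death individually.

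Protocol section 6 describes a longer window: "safety analyses will be performed on data for patients through the Week 52 assessments or early discontinuation". Rescue is not discontinuation. Protocol 3.1.1, on rescue from Week 12 onward, says: "An early withdrawal visit is not required for a patient to receive rescue therapy, and patients should continue to be followed in the study". Protocol 5.3.1 has all adverse events reported throughout the treatment period. Protocol 6.2.1 (safety population) and 6.6 (safety analyses) contain no cut at rescue. SAP 4.5 cuts each patient's data at the Week 52 visit or early withdrawal, again without mention of rescue.

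**The concern.** Rescue follows treatment failure, so it is an outcome of randomised treatment. A table that stops at rescue truncates follow-up on that outcome, possibly by different amounts in the two arms. It is then no longer a comparison of the groups as randomised over the planned period.

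Events after rescue can still bear on the assigned treatment. Under Protocol 3.1.1 and 4.4.2, only rescue with rituximab between Weeks 12 and 24 cancels the Day 168 and Day 182 infusions. A patient rescued earlier with something else may still receive the blinded infusions, and whether MMF or its placebo continues is left to consideration case by case. An infusion reaction or infection after a randomised Day 168 infusion could therefore fall outside the main tables.

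At stake is a basic safety result: how many patients in each arm had a serious adverse event or an infection during the 52 weeks.

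**Working it through.** **Is there a combined table?** The rule, the window and the outputs, side by side:

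| Source | End of the safety window | Post-rescue events |
|---|---|---|
| Protocol 6 | Week 52 or early discontinuation | no exclusion stated |
| SAP 4.5 | Week 52 visit or early withdrawal | no exclusion stated |
| SAP 4.2, 4.9 | rescue, for rescued patients | separate summaries, selected outputs |
| SAP 4.2, 4.9.2, 4.9.3 (listings) | none at rescue | included |
| Follow-up SAP 3.2.1, 3.6 | safety follow-up | rescued patients analysed separately |

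SAP 4.9.2 names no by-arm summary that joins pre- and post-rescue events, and the follow-up SAP adds none.

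**Can the tables be added?** Let A be the patients in an arm with an event before rescue, B those with one after, and C those with both. The number with at least one event is A + B − C. The two tables give A and, where the output is selected, B. C needs patient-level data, so A + B overcounts by C.

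**How much follow-up is dropped?** The plan gives no rescue rate or timing, so there is no figure to reproduce. Every rate below is an assumption, with all patients otherwise followed to Week 52.

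Share dropped = r × (52 − t)/52, where r is the proportion rescued and t the mean week of rescue. With about 132 patients randomised 1:1, each arm has about 66 patient-years over 52 weeks.

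| Assumption | Rituximab dropped | MMF dropped |
|---|---|---|
| r = 5–10% and 10–25%, t = 26 (factor 0.5) | 2.5–5% (1.65–3.3 patient-years) | 5–12.5% (3.3–8.25) |
| r = 2% and 10%, t = 32 (factor 20/52) | 0.8% (0.5) | 3.8% (2.5) |
| r = 10% and 30%, t = 32 | 3.8% (2.5) | 11.5% (7.6) |
| every assumed non-responder (35%, 60%), t = 32 | 13.5% (8.9) | 23.1% (15.2) |

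Week 32 is the midpoint of the Week 12–52 rescue window. The last row takes 1 − 0.65 and 1 − 0.40 from the sample-size section and is an extreme.

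**Do rates repair this?** SAP 4.9.2 allows rates per 100 patient-years if exposure is unbalanced, but does not say which exposure. In SAP 4.9.1, rituximab exposure runs to Week 52 or early withdrawal and is not cut at rescue. MMF exposure runs to the last MMF administration.

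Suppose the true rates are constant and equal, counts stop at rescue, and both denominators run to Week 52. The apparent rituximab/MMF ratio is (1 − d_R)/(1 − d_M), where d_R and d_M are the dropped shares for rituximab and MMF:
- t = 26: from 0.95/0.95 = 1.00 to 0.975/0.875 = 1.11.
- The three rows at t = 32: 1.03, 1.09 and 1.13.

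If MMF dosing ended at rescue, the MMF rate would be consistent while the rituximab rate would not. At t = 26 the ratio would then be 1 − d_R, or 0.95 to 0.975. The direction of the error depends on a denominator the SAP leaves open.

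**The case against.** The strongest defence is that a to-rescue comparison is legitimate. Rescue may be open-label rituximab, so MMF-arm patients can receive the test drug, and the protocol groups safety by treatment received. Stopping the main table at rescue keeps those events from being charged to MMF. That stands, and it is why the to-rescue tables should stay. It does not argue against a second set.

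A reader might infer that the SAP plainly breaches the protocol. The text does not go that far. The sentence in Protocol section 6 can be read as fixing the data cut for the first reporting event, and the same section leaves methods to the SAP. What can be said is that the SAP adds a restriction that neither Protocol section 6 nor SAP 4.5 contains.

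A reader might also infer that post-rescue events go unreported. They do not: listings are complete, deaths are listed individually, selected summaries are planned, and SAP 4.10.1 presents all displays by treatment group. With about 132 patients, someone could derive the full counts from the listings. The gap is the missing table.

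Two supporting arguments must be kept within their limits. Protocol 3.3.1 calls the rituximab dose "sufficient to sustain B-cell depletion for 6–9 months", but that statement is about rheumatoid arthritis and is not evidence on duration in pemphigus. And the 65% and 40% figures are remission rates: they make unequal rescue plausible but do not establish it. With equal rescue at the same mean time, the two arms lose the same share and the rate ratio above is 1.00 when both denominators run to Week 52.

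**Conclusion.** The point holds as a gap in the planned outputs. The SAP truncates the main Week 52 safety tables at an outcome-dependent event, without a basis stated in the protocol, and plans no table of patients per arm with an adverse event, serious adverse event or infection over 52 weeks.

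The size is unknown because no rescue rate is given. On the Week 26 assumptions the loss is modest: 2.5–5% of rituximab and 5–12.5% of MMF person-time. A rate with mismatched exposure could be off by up to about 11% on those assumptions. It would also be an inference, not something the documents show, that the dropped time belongs to the sickest or most immunosuppressed patients. The primary efficacy result is not affected. The change should be made because the data are already collected and the missing count is one that readers of the safety results will look for.

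**What to change.** Keep the to-rescue tables. Beside them, add by-arm tables of adverse events, serious adverse events, infections and serious infections through Week 52 or early withdrawal regardless of rescue. Deaths need no new table, since they are already listed individually. In the added tables, flag events that start after rituximab or MMF rescue. In SAP 4.9.2, define the exposure denominator for each set: time to rescue for the to-rescue tables, time to Week 52 or early withdrawal for the full-period tables, by the same rule in both arms. State in SAP 4.2 and 4.9 how the rescue cut relates to Protocol section 6 and SAP 4.5.

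The cost is a few extra tables from existing data, with no change to patient management. The downside is that MMF-arm events after rituximab rescue enter the full-period tables, so the flag is needed to keep them from being read as MMF effects.
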